9.1.3 Early stopping for safety and feasibility

The study will also be stopped any time for safety. If 3 or more subjects have a grade 4 or 1 subject has grade 5 toxicity probably or definitely treatment related toxicity while on therapy or within 3 months off the therapy, the trial will be stopped early for lack of safety.

Interim Monitoring for Feasibility

Primary early monitoring for feasibility will be based on the short-term feasibility endpoint that at least 60% of doses are administered to the subject, as assessed at 16 weeks. Less than 60% of doses administered for any reason constitutes an unacceptable level of dosing. An acceptable feasible outcome would be the successful administration of the study therapy to 80% or more of subjects at 16 weeks. Treatment compliance will be assessed in each cohort (children with or without NF1) when 4 patients have been accrued and completed the first 16 weeks of treatment. Failure to administer $\geq 60\%$ of doses in this interval in three out of the four patients will result in suspension of accrual to that cohort.

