Relationship/attribution: The Investigator will be asked to document his/her opinion of the relationship of the event to study medication as follows:

- 1) *Unrelated*: The adverse event is clearly not related to the investigational agent(s).
- 2) *Unlikely*: The adverse event is doubtfully related to the investigational agent(s).

- 3) *Possible*: The adverse event may be related to the investigational agent(s).
- 4) *Probable*: The adverse event is most likely related to the investigational agent(s).
- 5) *Definite*: The adverse event is clearly related to the investigational agent(s).

10.1: Reporting Adverse Drug Reactions Occurring with Investigational Agents

Within 24 hours of recognition, contact the Principal Investigator or his designee by telephone to verify the identification process and the existence of an adverse drug reaction or toxic death.

The following data **must** be reported to the study PI:

- Subject identification number
- Presenting diagnosis, Description of event
- Laboratory data supporting event
- Total and daily doses of suspected drug
- Time of event
- Type and grade of adverse event
- Methods used to recognize and characterize the effect
- Physician attribution/relationship of event to study drug (see above)

The participating site must then submit a completed adverse event case report form to the coordinating site.

Within 10 days of the adverse event, a completed NCI Adverse Reaction Form for Investigational Agents with the NCI protocol number should be submitted to the IRB for life threatening (Grade 4) and fatal known reactions (except Grade 4 myelosuppression) or any unexpected, unanticipated Grade 2 and 3 reactions that are possibly, probably, or definitely attributed to the study drug.

A completed (NCI) Adverse Reaction Form for Investigational Agents should be sent electronically or by FAX to the FDA (see Appendix IV for the electronic links). Oncovir will be notified as soon as an adverse event form has been submitted.

10.2: Toxicity Criteria.

The NCI Common Terminology Criteria for Adverse Events (CTCAE) version 4.0 will be used and referenced. The site, measure, grade, relationship, action taken, and outcome for all toxicities (grades 3 and 4 as well as any unexpected, unanticipated Grade 2 reactions that are possibly, probably, or definitely attributed to the study drug) are to be reported on the appropriate toxicity monitoring and adverse event forms.

10.3: Data Safety Monitoring

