10.3.1 Data and Safety Monitoring Board

This study will be monitored in accordance with the UCSD/Rady Children's Hospital plan for data and safety monitoring of Phase 1 and 2 studies. This study will use the UCSD Moores Cancer Center DSMB. In brief, the role of the Data and Safety Monitoring Board is to protect the interests of patients and the scientific integrity for all Phase 1 and 2 studies. The DSMB consists of 7 members including a chair, a statistician, and a pharmacist. The DSMB meets on a regular basis to review current study results, as well as data available to the DSMB.

from other related studies. The DSMB will provide recommendations for each study reviewed to change the study or to continue the study unchanged. Data and Safety Board reports for institutional review boards will be prepared.

10.3.2: Study Monitoring

The Principal Investigator will monitor the study regularly to validate subjects' eligibility, evaluability, and any toxicities that are entered in the study database. In addition, the study committee comprised of the coordinating site members and at least 2 members of the participating site via phone conference will discuss and review once a month the enrolled subjects, toxicities, and integrity of data collection.

Monitoring of Source Documents:

The participating site will submit case report forms and copies of necessary supporting clinical source documents to the coordinating site for review of data accuracy prior to data submission. This will occur at a monthly interval from the time of subject's enrollment into the study.

Additionally a member of the DSMB at the coordinating site will monitor the data collection and the source documentation of all subjects enrolled at the enrolling sites. This monitoring will review protocol compliance, drug accountability, and adverse event reporting as well as regulatory compliance annually.

10.4: FDA Annual Reporting

Oncovir, the IND holder of the study drug, will submit an annual report to the FDA. This report will include de-identified aggregate data from this study as well as compiled NCI adverse event reports.

11.0: REFERENCES

Black K, K. Chen, et al. (1992). Inflammatory leukocytes associated with increased immunosuppression by glioblastoma. *Journal of Neurosurgery* 77:120-126.

Blyth CR, Still HA (1983). Binomial confidence intervals. *Journal of the American Statistical Association* 78:108-116.

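### The numeric safety stop leaves out a death rated only possibly related, and the protocol text ties no accrual pause or prompt DSMB review to such a death

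*Combined protocol and SAP*

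**What the plan says.** Section 9.1.3 opens with a general statement, "The study will also be stopped any time for safety", which gives no criterion and names no decision-maker. The numeric rule follows: the trial stops when "3 or more subjects have a grade 4 or 1 subject has grade 5 toxicity probably or definitely treatment related toxicity while on therapy", also counting the 3 months after leaving therapy.

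Section 10.0 sets out five attribution levels: unrelated, unlikely, possible, probable, definite. The rating is personal to the Investigator: "The Investigator will be asked to document his/her opinion of the relationship of the event to study medication". 'Possible' is the level at which the event may be drug-related.

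The steps that follow a serious event are these:
- Section 10.1: "Within 24 hours of recognition, contact the Principal Investigator or his designee by telephone", in order to verify that the reaction or toxic death occurred. A case report form then goes to the coordinating site, and the IND holder is told once the adverse event form is submitted.
- Section 10.1: within 10 days, a form "should be submitted to the IRB for life threatening (Grade 4) and fatal known reactions (except Grade 4 myelosuppression", the last being an exception).
- Section 10.0: serious adverse events are reported to the FDA whatever their attribution.
- Section 10.3.2: a study committee with members from both sites reviews toxicities monthly.
- Section 10.3.1: "The DSMB meets on a regular basis to review current study results", under an institutional "plan for data and safety monitoring of Phase 1 and 2 studies" that is not reproduced.

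**The concern.** Whether one death ends the trial under the numeric rule can turn on the choice between 'possible' and 'probable'. In this disease that choice may be hard. Section 7.0 warns that MRI interpretation is confounded, and section 8.1 reports transient enlargement of enhancing disease during poly-ICLC and allows treatment past conventional progression. A death with both tumor and drug as candidate causes could reasonably be rated possible.

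At stake is whether an independent body looks at that rating before the next child is enrolled. The protocol does hold accrual in other situations: after 14 subjects until the six-month results are known (9.1.1), and in a cohort where dosing falls short (9.1.3). It specifies no hold for a possibly drug-related death.

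**Working it through.** **Text, side by side**

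| Question | Where | Answer for a death rated possible |
|---|---|---|
| Does it count toward the numeric stop? | 9.1.3 with 10.0 | No; only probable or definite counts |
| Who is told? | 10.0, 10.1 | Principal Investigator (24 hours), coordinating site, IRB (10 days, known fatal reactions), FDA, IND holder; the DSMB is not named |
| Who reviews, and when? | 10.3.1, 10.3.2 | Study committee monthly; DSMB at an unstated regular interval |
| Is accrual paused? | 9.1.1, 9.1.3 | The only specified holds are for six-month results and for dosing |

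**Illustrative size.** The plan gives no operating characteristic for the safety rule, so there is no figure of its own to reproduce. It also gives neither a drug-caused death rate nor the share of such deaths rated possible. Section 2.3 reports two grade 5 events in adult studies, neither assessed as related, and no dose limiting toxicity in 45 children. The inputs below are therefore assumptions: a drug-caused death rate q of 1% or 2% per subject, with half rated possible. The numbers of subjects, 14 and 23, come from 9.1.1.

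Probability that the death trigger fires: all such deaths counted, 1 − (1 − q)^n; half counted, 1 − (1 − q/2)^n.

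| n | q | All counted | Half counted | Difference |
|---|---|---|---|---|
| 23 | 2% | 1 − 0.98^23 = 0.372 | 1 − 0.99^23 = 0.206 | 0.165 |
| 23 | 1% | 1 − 0.99^23 = 0.206 | 1 − 0.995^23 = 0.109 | 0.097 |
| 14 | 2% | 1 − 0.98^14 = 0.246 | 1 − 0.99^14 = 0.131 | 0.115 |
| 14 | 1% | 1 − 0.99^14 = 0.131 | 1 − 0.995^14 = 0.068 | 0.063 |

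Differences are taken before rounding. If none were rated possible, the loss would be zero. If all were, the trigger would never fire.

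**How often the added pause would act.** Under the same assumptions, the difference column is the chance that a trial has a possibly related death and no death that already stops it. The plan puts the chance of stopping at 14 under the null at 61%; the exact binomial value, P(X ≤ 7) with n = 14 and p = 0.5, is 60.5%. Weighting by 61%:
- q = 1%: 0.61 × 0.063 + 0.39 × 0.097 ≈ 0.08
- q = 2%: 0.61 × 0.115 + 0.39 × 0.165 ≈ 0.13

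This treats deaths as independent of the stage 1 result. It omits tumor deaths rated possible, which would add pauses. It includes deaths after accrual has closed, which would pause nothing.

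**Pace of accrual.** 23 subjects in 36 months is 0.64 a month (9.1.6); 15 a year is 1.25 a month (3.1). About one child enrols between monthly committee reviews.

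**Grade 4 wording.** In the rule sentence, 'grade 4' has no noun or attribution of its own. The natural reading applies 'probably or definitely' to both grades; the other counts grade 4 of any cause. The rules differ. With invented rates of 15% for any grade 4 and 5% for related grade 4, P(at least 3 of 23) is 0.69 or 0.11.

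**The case against.** A probable-or-definite threshold for automatic termination, with wider thresholds for reporting, is a coherent design. Termination after one death is drastic, and limiting it to clearer attributions avoids ending a trial because of the tumor. That stands, and it is why the termination rule should stay as it is.

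A reader might infer that a possibly related death would pass unexamined, or that one person's opinion settles the matter. The documents do not support that. The Principal Investigator must verify the event within 24 hours with supporting data, FDA reporting does not depend on attribution, a two-site committee sees toxicities monthly, and the general safety sentence permits a stop at any time. What remains is narrower: the Principal Investigator's check is not independent if that person is also the treating Investigator, the committee is not the DSMB, and the general sentence has no criterion.

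The strongest objection is that the institutional monitoring plan cited in 10.3.1 may already require prompt DSMB review after a death. That cannot be excluded. What can be shown is only that the protocol text does not contain or point to such a trigger.

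It is also fair that no death rate or 'possible' share used above has a source.

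**Conclusion.** The point holds in a limited form. The numeric stop does not count a death rated only possibly related, and the protocol text attaches no accrual pause or prompt DSMB attribution review to it. This rests on the wording of 9.1.3, 10.0, 10.1 and 10.3, and on no assumed rate.

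The practical size is unknown. The trigger probabilities are illustrative and should not be read as a finding that the rule loses about half its sensitivity; that follows only from assuming that half of drug-caused deaths are rated possible. Nor would the fix recover the whole difference, since the DSMB would not upgrade every such death. Existing safeguards limit the harm, and the toxicity experience in section 2.3 suggests that drug-caused deaths would be rare.

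The grade 4 ambiguity is a minor wording matter. It does not show that the grade 4 arm is defective and adds no weight to the main point. Overall this is a cheap improvement for the sponsor to consider, held with medium confidence because the institutional plan is not shown.

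**What to change.** Leave the termination rule unchanged for events that the Investigator rates probably or definitely related. Add to 9.1.3:

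> A grade 5 event rated possibly related, on therapy or within 3 months off therapy, pauses accrual until the existing DSMB has reviewed attribution. If the DSMB judges it probably or definitely related, it counts toward the stopping rule. The DSMB review may raise but not lower the Investigator's attribution for this rule.

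The last sentence matters: without it, the review could be used to downgrade a death that now stops the trial. If the institutional monitoring plan already has an equivalent trigger, cite it in 9.1.3 instead. Separately, have the sponsor confirm the intended rule for grade 4. If attribution is meant to apply to both grades, say so.

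The change needs a few sentences and no new body. Its cost is an occasional short accrual pause for a death that proves tumor-related. On the illustrative rates, a pause without an existing stop would arise in roughly 8% to 13% of trials under the null, excluding tumor deaths rated possible. The choice between 'unlikely' and 'possible' stays with the Investigator, so dependence on attribution is reduced but not removed.

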4.0 Study Treatment

4.1 Treatment Schedule

Children will receive poly-ICLC 20 mcg/kg/dose twice weekly IM (using Monday/Thursday or Tuesday/Friday schedule if possible). The first 2 doses will be administered in the clinic under supervision.

Vital signs will be monitored every 30 minutes for 2 hours after the first dose. For all subsequent doses administered at home, a temperature log will be kept to document the temperature prior to study drug administration and at two separate time points after each of the 8 doses of study drug in cycle 1. One temperature reading will be assessed between hours 2-4 after study drug administration and one temperature reading will be assessed at 12 hours after study drug administration. After cycle 1, temperature will only be monitored on an as needed basis, such as if the subject is not feeling well. Subjects or their parents will be instructed to use a log to record the temperature monitored at home and any fever should be reported to the study team. In some cases, at the discretion of the research team, subject or parent will be allowed, after appropriate teaching, to administer the study drug at home. The study drug will be dispensed to the subject/parent by the research pharmacy. The study drug will be dispensed in vials along with labeled dose syringes in order to minimize errors in dosing.

Total length of treatment will be two years. Each cycle will be 28 days in length. If subjects demonstrate a response to therapy (see section 7.0), treatment may be continued beyond two years at the discretion of the principal investigator and pending drug availability. For statistical analysis of toxicity, subjects will be divided into two separate cohorts (those with NF1 and those without NF1). The subjects in each of these cohorts will be treated and monitored identically throughout treatment.

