Subjects who travel to the coordinating or enrolling sites for protocol therapy may return home to the care of their primary pediatric oncologist after completing cycle 1 of therapy for standard of care management at the discretion of the study physician/committee. Subjects will be seen and monitored by their primary treating oncologist at the start of each cycle. For those subjects, a 3 month supply of study drug will be dispensed to the subject/family from their enrolling site. The enrolling site will continue to see the subject every 3 months for evaluation and will remain responsible for continued data capture of all required information.

4.2: Dose modifications based on Toxicity

If AST/ALT > 10x ULN while on study, Poly ICLC will be discontinued until the AST/ALT are < 5x ULN; the study drug will then be restarted at 20 mcg/kg/dose twice weekly (the initial dose).

If AST/ALT > 10x ULN for a second time, hold study drug until values < 2.5x ULN; then restart drug at the reduced dose of 10 mcg/kg/dose twice weekly.

Study drug will be stopped and subject will be off treatment for toxicity if AST/ALT do not decrease to < 5x ULN during the first episode and <2.5x ULN at second episode when drug is held for three weeks.

For the NF 1 cohort, consider restarting drug again at 5 mcg/kg/dose twice weekly if toxicities recur at the prior reduced dose of 10mcg/kg/dose.

For all other grade 3 or grade 4 toxicities the same dose modifications will be followed. The study drug will be held until resolution of these toxicities to ≤ grade 1. If the toxicity is not resolved within 3 weeks of the last dose of the study drug administration the subject will be taken off protocol therapy.

4.3: Concomitant Therapy

Corticosteroids and anticonvulsants may be given as indicated clinically. However, if the dose of steroids is increased while on therapy, MRI must be performed to rule out disease progression. Acetaminophen may be given as needed to control poly-ICLC side effects. A non-P450 inducing anticonvulsant will be used while on this study (see Appendix 3).

Radiotherapy may not be given while on study to the lesions being utilized as measurable disease in order to assess response. Patients may enter on study after completion of involved field radiation therapy, however at least 8 weeks should elapse after radiation, and scans should show residual disease prior to entry on study. Chemotherapy is not allowed.

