8.0 CRITERIA FOR REMOVAL FROM PROTOCOL THERAPY AND OFF STUDY CRITERIA

8.1 Criteria for Removal from Protocol Therapy

a. Progressive disease

Note: Transient enlargement of enhancing disease with subsequent shrinkage has been reported during poly-ICLC treatment. Because of this, if the patient has progressive disease by the conventional definition above but does not have unacceptable progression by the definitions below, the treating physician and patient have the options of continuing poly-ICLC treatment on this protocol or of discontinuing treatment.

b. Criteria for unacceptable progression: See definitions of tumor progression outlined in section 7.1.3

1. >50% increase in the product of the three perpendicular diameters of initial tumor relative to the initial baseline measurement – LxWxT (current can) $> 1.5 \times$ LxWxT (initial scan), or the development of any new sites of disease independent of the response of the initial tumor. Post radiation changes are often seen on post-treatment imaging studies, so that classification of a patient as having progressive disease may require several serial MRI's if the child has received radiation within the preceding 12 months.

2. Unacceptable worsening of neurological symptoms that cannot be controlled with corticosteroids.

3. Any other radiological or clinical evidence of worsening to the extent that the treating physician feels it is not in the patient's best interest to continue poly-ICLC.

c. Physician determines it is in patient's best interest.

- d. Patient and/or parent/guardian refusal to continue or inability to comply with protocol
- e. Grade 3 or 4 toxicity that does not resolve to Grade 1 within three weeks after interruption of therapy, or recurrent grade 3 or 4 toxicity at a reduced dose level (see section 4.2).

Note: If final analysis confirms a beneficial effect of poly-ICLC, and/or if tumor recurs after withdrawal from poly-ICLC at the end of the 2-year prescribed treatment period, participating subjects may be offered continued treatment with poly-ICLC (subject to drug availability at that time).

- f. Completion of planned therapy.

Subjects who are off protocol therapy are to be followed until they meet the criteria for Off Study (see below). Follow-up data will be required, unless consent is withdrawn, every 3 months for the first year, every 4 months for the second year, every 6 months for the third year, and then yearly thereafter

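### Section 9.1.3 counts under-dosing for any reason as failure, but sets the feasibility look on patients who completed 16 weeks of treatment, so it is unclear whether early stoppers count

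*Combined protocol and SAP*

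**What the plan says.** Section 9.1.3 (Interim Monitoring for Feasibility) defines the patient-level endpoint as "at least 60% of doses are administered to the subject, as assessed at 16 weeks". It adds: "Less than 60% of doses administered for any reason constitutes an unacceptable level of dosing". An acceptable outcome for the study is "successful administration of the study therapy to 80% or more of subjects at 16 weeks".

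The look takes place in each cohort (with and without NF1) "when 4 patients have been accrued and completed the first 16 weeks of treatment". Failure to reach 60% "in three out of the four patients will result in suspension of accrual to that cohort".

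Three other places bear on this:

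- Section 4.1 sets dosing at "twice weekly IM (using Monday/Thursday or Tuesday/Friday schedule if possible") and allows home injection by the subject or parent.
- Section 4.2 limits a toxicity hold: "If the toxicity is not resolved within 3 weeks of the last dose of the study drug administration the subject will be taken off protocol". Section 8.1(e) also removes a child for "recurrent grade 3 or 4 toxicity at a reduced dose level (see section 4.2"). For the NF1 cohort only, section 4.2 mentions a possible further restart.
- Section 9.1.5 puts everyone with at least one dose in the analysis population. It counts an endpoint that cannot be assessed against the therapy, with an early drop for toxicity as its example.

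**The concern.** The definition of failure and the group it is tested on do not match. The definition covers a child who stops early for toxicity, refusal or progression. The trigger speaks of completing 16 weeks of treatment, not of 16 weeks having passed since the first dose. A child taken off therapy at week 3 has not completed 16 weeks of treatment, so on a literal reading another child takes that place among the four.

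The rule exists to pause a cohort in which the regimen cannot be delivered. If the four are chosen by whether they stayed on treatment, they are selected on something close to the outcome being measured. Heavier early drop-out would delay the look and would not show in its result. The plan also does not state the denominator for a child who stopped: all doses planned for 16 weeks, or only those due while on treatment.

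**Working it through.** The plan gives no operating characteristic for this rule, so there is no stated figure to reproduce.

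**Doses.** Twice weekly (section 4.1) for 16 weeks is 2 × 16 = 32 planned doses. 60% of 32 is 19.2, so 20 or more passes and 19 or fewer fails (at least 13 missed). On full dosing, dose 20 falls at about week 10. A child who stops at the end of cycle 3, when the first scheduled on-treatment MRI is done, has had 12 × 2 = 24 doses (75%) and passes against 32. Only stops before dose 20 are therefore at issue.

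**Can toxicity holds make a completer fail?** A hold of up to three weeks (section 4.2) costs 5 to 6 doses.

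- Two full holds: 32 − 12 = 20 (62.5%) to 32 − 10 = 22 (68.8%). Both pass.
- Three full holds: 32 − 18 = 14 (43.8%) to 32 − 15 = 17 (53.1%). Both fail.

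For one toxicity sequence outside NF1, section 4.2 allows two holds, the second followed by restart at a reduced dose. Recurrence at the reduced dose means removal under 8.1(e). A non-NF1 completer on one such sequence therefore does not fail through holds alone. The remaining routes are mainly missed home doses, and in NF1 a third hold.

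**Chance of suspension.** Let f be the true share of treated children receiving under 60% of doses, and e the share of those failures that are early stops. Both are assumptions, because the documents give neither. For simplicity, all early stops are taken to occur before dose 20.

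- Counting all treated children, the failure rate is f.
- Counting completers only, it is m = f(1 − e) / (1 − fe).
- With q the relevant rate, P(at least 3 of 4 fail) = 4q³(1 − q) + q⁴.

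| f | e | m | P(suspend), all treated | P(suspend), completers only |
|---|---|---|---|---|
| 20% | 80% | 0.04/0.84 = 4.8% | 2.7% | 0.04% |
| 30% | 80% | 0.06/0.76 = 7.9% | 8.4% | 0.2% |
| 50% | 60% | 0.20/0.70 = 28.6% | 31.3% | 7.3% |
| 50% | 80% | 0.10/0.60 = 16.7% | 31.3% | 1.6% |
| 50% | 100% | 0 | 31.3% | 0 |

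**Delay.** Under the completers-only reading, the expected accrual needed for four completers in a cohort is 4/(1 − fe). At f = 50% this is 4/0.70 = 5.7, 4/0.60 = 6.7 and 4/0.50 = 8 for e = 60%, 80% and 100%.

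**The case against.** A reader might infer that the plan definitely leaves early stoppers out and that the rule can hardly fire. The documents do not support that.

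- No sentence excludes early stoppers. The trigger phrase can be read as timing only: four patients have passed the 16-week point. The any-reason sentence in the same paragraph favours that reading.
- Section 9.1.5 also leans that way, as does section 9.1.1, which counts a Stage 1 subject who goes off study early for toxicity as a non-response.
- Section 9.1.3 describes the look as a check of treatment compliance. With home injection allowed, missed doses could fire the rule even among completers.
- The failure rates are assumed. The paediatric experience reported in section 2.3 is no dose-limiting toxicity in 45 children at 20-30 micrograms/kg twice weekly. At the acceptable limit of 20% failure the rule seldom fires on either reading (2.7% against 0.04%), because three of four is a high bar.
- The safety stop in 9.1.3, the monthly committee review and the DSMB (section 10.3) would probably notice heavy drop-out.

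Most of this stands, and it makes the point an inconsistency rather than a demonstrated exclusion. It does not remove the inconsistency. Section 9.1.5 says how to score a subject whose endpoint cannot be assessed. It does not say which four children form the look, and an early stopper's dose count can in fact be assessed. The Stage 1 sentence concerns PFS6, and the feasibility rule has no counterpart. The other safeguards do not apply the 60% criterion.

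A reader might also infer that the NF1 cohort is the smaller one and may never reach four completers. The documents give no cohort sizes. Section 2.2 reports more side effects in neurofibromatosis patients, particularly fever and erythema, but says nothing about discontinuation.

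**Conclusion.** The point holds as an internal inconsistency in section 9.1.3 that should be resolved before the rule is used. On one reading an early stopper is a dosing failure. On the literal reading of the trigger that child is not assessed at all, and the rule then loses most of its sensitivity to early discontinuation.

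The dose arithmetic follows from the plan, given the limits on holds in one non-NF1 toxicity sequence. The probabilities are illustrations that rest on assumed failure and drop-out shares. The gap is material when failure is common (31% against 7.3% or 1.6% at 50% failure) and small in absolute terms near the plan's acceptable level. Stops after dose 20 are not dosing failures on the 32-dose count. A claim that the rule is disabled would go too far, since the text permits the inclusive reading and missed home doses can still trigger suspension.

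**What to change.** Replace the trigger in section 9.1.3 with wording to this effect: dosing feasibility is assessed in each cohort on its first four treated subjects, once 16 weeks have elapsed from each one's first dose, whether or not the subject is still on treatment. The denominator is the 32 doses planned for that period, and doses not given after discontinuation count as not administered. Leave the 60% and three-of-four limits unchanged.

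This costs a sentence or two and needs no new data. The small downside is that the rule may fire somewhat more often and earlier, including for stops due to progression before dose 20. The any-reason definition already covers those.
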